7.5 Calculation or derivation of pharmacodynamic variables

7.5.1 Population analysis of pharmacokinetic/pharmacodynamic variables

The plasma concentration data for AZD9291 (and the metabolites AZ5104 and AZ7550) will be analysed using a population pharmacokinetic approach, which may include exploring the influence of covariates on PK, if the data allows. A population pharmacodynamic approach will be used to investigate the relationship between PK and selected primary, secondary and/or exploratory endpoints, where deemed appropriate. Results may be reported separately from the Clinical Study Report for the main study.

The pharmacokinetic, pharmacodynamic, demographic, safety and tumour response data collected in this study may also be combined with similar data from other studies and explored using population pharmacokinetic and/or pharmacokinetic-pharmacodynamic methods. The results of any such analyses will be reported separately from the Clinical Study Report.

7.6 Calculation or derivation of exploratory research variables

Results from the exploratory biomarker and pharmacogenetic research, and PROs may be reported separately from the Clinical Study Report for the main study.

7.7 Calculation or derivation of tumour response variables

For the investigator's assessment, at each visit patients will be programmatically assigned a RECIST visit response of CR, PR, SD or PD depending on the status of their disease compared to baseline and previous assessments.

Progression of TLs will be calculated in comparison to when the tumour burden was at a minimum (ie, smallest sum of diameters previously recorded on study). In the absence of progression, tumour response (CR, PR, SD) will be calculated in comparison to the baseline tumour measurements obtained before starting treatment.

If a patient has had a tumour assessment, which cannot be evaluated, then the patient will be assigned a visit response of not evaluable (NE) unless there is evidence of progression in which case the response will be assigned as PD.

Revised Clinical Study Protocol Drug Substance AZD9291 Study Code D5160C00001 Edition Number 3 Date

For TL measurements, if $\leq 1/3$ of the TL sizes are missing then a scaling up rule will be applied as follows:

- If $\leq 1/3$ of lesions recorded at baseline are missing then the results will be scaled up (based on the nadir sizes) to give an estimated sum of diameters and this will be used in calculations (this is equivalent to comparing the visit sum of diameters of the non-missing lesions to the nadir sum of diameters excluding the lesions that are missing and determining at what rate the lesions are changing)
- If > 1/3 of lesions recorded at baseline are missing then the TL response will be NE. However, if the sum of non-missing TL diameters would result in PD (ie, if using a value of 0 for missing lesions the sum of diameters has still increased by 20% or more compared to the smallest sum of diameters on study, with an absolute increase of \geq 5mm), PD takes precedence over NE
- A visit response of CR will not be allowed if any of the TL data is missing

For endpoints assessed by Independent Central Review, review of all radiological imaging data will be carried out using RECIST version 1.1. All radiological scans for all patients (including those at unscheduled visits, or outside visit windows), will be provided to the ICR. Prior radiotherapy and biopsied lesion reports for patients (at baseline) will also be provided to the ICR to allow the selection of appropriate target lesions. The imaging scans will be reviewed by two independent radiologists, using RECIST 1.1 criteria and will be adjudicated if required. For each patient, the ICR will define the overall visit response data (CR, PR, SD, PD or NE) and the relevent scan dates for each time point (i.e. for visits where response or progression is/is not identified).

7.7.1 **Objective response**

Objective response rate is defined as the percentage of patients who have at least one confirmed response of CR or PR prior to any evidence of progression (as defined by RECIST 1.1).

A visit response of CR is defined when all TL and NTL lesions present at baseline have disappeared (with the exception of lymph nodes which must be <10mm to be considered non-pathological) and no new lesions have developed since baseline. A visit response of PR is defined when the sum of diameters of the TLs has decreased by 30% or more compared to baseline (with no evidence of progression) and the NTLs are at least stable with no evidence of new lesions. A confirmed response of CR/PR means that a response of CR/PR is recorded at one visit and confirmed by repeat imaging at least 4 weeks later with no evidence of progression between confirmation visits.

In the case of stable disease, measurements should have met the stable disease criteria for a minumum interval of 5 weeks (6 weeks minus the 7-day visit window) following the start of treatment.

When the investigator is in doubt as to whether progression of disease has occurred and therefore reassesses the patient at a later date, the date of the initial scan should be declared as the date of progression if the repeat scans confirm progression.

For the extension cohort, ORR rate is defined as the number (%) of subjects with measurable disease with at least one visit response of CR or PR that is confirmed at least 4 weeks later (according to ICR for the primary analysis). Data obtained up until progression, or last evaluable assessment in the absence of progression, will be included in the assessment of ORR. However, any complete response or partial response which occurred after a further anti-cancer therapy was received will not be included in numerator of the ORR calculation.

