5.1.7 Duration of therapy

Patients should continue on treatment with AZD9291 until RECIST 1.1 defined progression or until treatment discontinuation criteria is met. There is no maximum duration of treatment as patients may continue to receive AZD9291 beyond RECIST 1.1 defined progression as long as they are continuing to show clinical benefit, as judged by the investigator.

If AZD9291 is discontinued for reasons other than disease progression, the patient must continue RECIST 1.1 assessments every 6 weeks until disease progression, even if further lines of anticancer therapy are administered.

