6.10 Anti-tumour activity

6.10.1 Tumour assessments

RECIST 1.1 guidelines for measurable, non-measurable, target lesions (TLs) and non-target lesions (NTLs) and the objective tumour response criteria are presented in Appendix F of this Clinical Study Protocol.

Baseline CT or MRI assessments of chest and abdomen (including liver and adrenal glands) must be performed no more than 28 days before the start of study treatment, and ideally

should be performed as close as possible to the start of study treatment. Additional imaging may be performed based on individual patient signs and symptoms. CT/MRI scan of the brain should be performed in patients with known or suspected brain mestastases.

The methods of assessment used at baseline should be used at each subsequent follow-up assessment. Follow-up assessments should be performed every 6 weeks (\pm 7 days) after the start of multiple dosing until objective disease progression as defined by RECIST 1.1 even if a patient discontinues treatment prior to progression.

Any other sites at which new disease is suspected should also be appropriately imaged. If an unscheduled assessment is performed and the patient has not progressed, every attempt should be made to perform subsequent assessments at the scheduled visits whilst the patient remains on study treatment.

Categorisation of objective tumour response assessment will be based on the RECIST 1.1 guidelines for response: CR (complete response), PR (partial response), SD (stable disease) and PD (progression of disease). Target lesion progression will be calculated in comparison to when the tumour burden was at a minimum (i.e. smallest sum of diameters previously recorded on study). In the absence of progression, tumour response (CR, PR, SD) will be calculated in comparison to the baseline tumour measurements obtained before starting treatment.

If the investigator is in doubt as to whether progression has occurred, particularly with response to NTLs or the appearance of a new lesion, it is advisable to continue treatment and reassess the patient's status at the next scheduled assessment or sooner if clinically indicated. If repeated scans confirm progression, then the date of the initial scan should be declared as the date of progression.

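### The ORR definition for the escalation and expansion cohorts does not exclude responses first seen after a further anticancer therapy; that exclusion is written for the extension cohort only

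*Protocol*

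**What the plan says.** Section 7.7.1 opens with a general definition of ORR: "the percentage of patients who have at least one confirmed response of CR or PR prior to any evidence of progression". Nothing in it refers to treatment started after AZD9291. The escalation and expansion cohorts have no other definition.

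A later paragraph of the same section is limited to one cohort. It begins "For the extension cohort, ORR rate is defined as the number (%) of subjects with measurable disease". Within that paragraph, a complete or partial response "which occurred after a further anti-cancer therapy was received" is left out of the numerator.

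On follow-up, Section 5.1.7 says, without limiting it to a cohort, that a patient who stops AZD9291 for a reason other than progression must "continue RECIST 1.1 assessments every 6 weeks until disease progression, even if further lines of anticancer therapy are administered". Section 6.10.1 likewise continues scans to objective progression "even if a patient discontinues treatment prior to progression". Sections 5.4.1 and 6.3.8.2 and Appendix F Section 4.5 agree. Appendix F Section 4.1 does not: it ends the follow-up scans when study treatment is discontinued or consent is withdrawn.

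Section 7.1 makes ORR primary for the extension and secondary for escalation and expansion. Section 7.2.2.1 uses the expansion ORR, with Clopper-Pearson intervals, to judge the prospects of future studies in each population. It treats zero confirmed responses as no evidence of activity.

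**The concern.** The protocol foresees that a patient may stop AZD9291 without progression, start another anticancer drug and still be scanned on schedule. For the extension it says how such a patient's later response is handled. For the other two parts the only cut-off is progression. A first confirmed response obtained on the next drug therefore meets the definition and is credited to AZD9291.

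Any error from this runs one way, because the definition can add responders who owe nothing to AZD9291 but cannot remove any. The same patients would also enter duration of response, since Section 7.7.3 builds on the confirmed response.

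What is at stake is the expansion ORR by population. The first-line cohort is the clearest case. These patients have had no prior therapy for advanced disease, and Sections 2.1 and 2.2 describe EGFR TKIs as established first-line treatment with clinical benefit in about 70% of patients with sensitising mutations. A first-line patient who stopped AZD9291 early for toxicity could respond to one of those agents.

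**Working it through.** **1. The two definitions side by side (Section 7.7.1).**

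| | Escalation and expansion | Extension |
|---|---|---|
| Confirmed CR or PR required | Yes | Yes |
| Cut-off at progression | Yes | Yes |
| Responses after further anticancer therapy | Not mentioned | Removed from numerator |
| Scans continue on further therapy (Section 5.1.7) | Yes | Yes |

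Section 7.9 adds no exclusion for escalation or expansion. Section 7.7 measures response against the baseline taken before AZD9291, so a later drug can produce a qualifying decrease.

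**2. How a patient is affected.** All of these must hold:
- AZD9291 is stopped without RECIST progression;
- there is no confirmed response already;
- another therapy starts before progression (Section 4.3.1 bars other anticancer agents during study treatment);
- CR or PR is then reached against the original baseline, which for PR means a decrease of at least 30%;
- it is confirmed at least 4 weeks later, with no progression in between.

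**3. The protocol's own expansion figures reproduce (Section 7.2.2.1).**
- Chance of no responses at a true rate of 30%: 0.7^30 = 0.0000225 (stated as below 1%) and 0.7^8 = 0.0576 (stated as below 6%).
- Clopper-Pearson 80% limits for x of n are the 10% quantile of Beta(x, n − x + 1) and the 90% quantile of Beta(x + 1, n − x). They give 5/30: 8.3% to 28.7%; 9/30: 19.0% to 43.2%; 15/30: 37.0% to 63.0%; 21/30: 56.8% to 81.0%. All agree with the protocol after rounding.

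**4. Effect of one such patient in a cohort of 30.** The change is 1/30 = 3.3 points.
- 9/30 = 30.0% (19.0% to 43.2%) becomes 10/30 = 33.3% (21.8% to 46.6%).
- At the boundary, 0/30 (0% to 7.4%) becomes 1/30 = 3.3% (0.4% to 12.4%).

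**5. How often, under assumed rates.** The protocol gives no switching rate. Let s be the proportion who switch before progression without a prior confirmed response, and q the proportion of those who then have a confirmed response. Mean inflation of ORR is s × q. The chance of at least one counted case among n patients is 1 − (1 − s × q)^n. I assume s from 3% to 10% and q from 20% to 40%.

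| s, q | Mean inflation | At least one, n = 30 | At least one, n = 8 |
|---|---|---|---|
| 3%, 20% | 0.6 points | 16.5% | 4.7% |
| 5%, 30% | 1.5 points | 36.5% | 11.4% |
| 10%, 40% | 4.0 points | 70.6% | 27.9% |

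The expected number of such patients in a cohort of 30 runs from 30 × 0.006 = 0.18 to 30 × 0.04 = 1.2. The last row is the extreme corner of the assumed range, not a forecast.

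**The case against.** The general definition is silent on later therapy; it does not say that such responses count. Inclusion follows from that silence together with the scan rule, and handling of scans after new therapy is often left to the analysis plan. The fuller wording for the extension also fits the place where ORR is primary. This stands in part: it is fair to say that the definition does not exclude these responses, and a reader should not infer that the sponsor deliberately chose to count them. It does not dispose of the point. The protocol states a rule for each part, and the two differ. An analysis plan that applied the exclusion everywhere would depart from the general definition as written. The exclusion sentence may have been meant for all cohorts, but its position does not say so.

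The route is narrow. Treatment normally runs to progression and may continue beyond it, and responses after progression are already excluded in every cohort. This stands, and it limits the weight of the point.

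A reader might infer that one such patient would overturn a finding of no activity. The arithmetic allows it, but the documents make it remote for the pre-treated T790M-positive cohorts: Sections 3.2 and 5.2 report objective responses from the 20 mg starting dose onwards. Closing a cohort early is optional and at the sponsor's discretion (Section 7.2.2.1). Zero responses remain conceivable in T790M-negative patients, so the scenario is unlikely rather than impossible.

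Appendix F Section 4.1, read alone, would largely close the gap by ending scans at discontinuation. It conflicts with Sections 5.1.7, 5.4.1, 6.3.8.2 and 6.10.1 and with Appendix F Section 4.5, so it cannot be relied on as a safeguard.

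**Conclusion.** The point holds, at minor severity. For escalation and expansion, the ORR definition followed as written credits AZD9291 with a first confirmed response obtained on a later drug, which the extension rule would remove. The bias can only be upward and is 3.3 points per patient at n = 30. Under the assumed rates above, mean inflation is 0.6 to 4.0 points. Those rates are mine, and the number of patients affected is probably small.

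The documents do not support the stronger inference that the expansion results are materially inflated. ORR is secondary and preliminary in these cohorts, and the intervals for 9/30 and 10/30 overlap almost entirely. Nor is the extension's primary ORR affected, because the exclusion is in place there. The reason to act is that the expansion ORR informs decisions on future studies population by population, and the two rules differ without a stated reason.

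The conclusion assumes that scans continue to progression, as most of the protocol says.

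**What to change.** Move the exclusion sentence from the extension paragraph of Section 7.7.1 into the general ORR definition, so that in every cohort a response first seen after a further anticancer therapy is left out of the numerator. The denominator needs no new rule: under Table 7 the response-evaluable set is defined by dosing and a baseline RECIST assessment, so these patients already stay in it.

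Reconcile Appendix F Section 4.1 with Sections 5.1.7, 5.4.1, 6.3.8.2 and 6.10.1 and Appendix F Section 4.5, so that one end point for the scan schedule is stated throughout.

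The cost is one relocated sentence and one harmonised schedule statement. Subsequent anticancer therapy is already recorded (Sections 4.3.1 and 6.3.8.2), and the sample size and interval method do not change.

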7.7.2 Progression Free Survival

PFS is defined as the time from date of first dosing until the date of objective disease progression as defined by RECIST 1.1 or death (by any cause in the absence of progression) regardless of whether the subject withdraws from AZD9291 therapy or receives another anti-cancer therapy prior to progression.

Patients who have not progressed or died at the time of analysis will be censored at the time of the latest date of assessment from their last evaluable RECIST assessment. If the patient has no evaluable visits or does not have baseline data they will be censored at 0 days unless they die within two visits of baseline.

If a patient discontinues treatment prior to progression and/or receives a subsequent therapy prior to progression then these patients will continue to be followed until evidence of objective disease progression as defined by RECIST 1.1 and their PFS time will be derived as defined above.

Note: Symptomatic deterioration will not be regarded as a progression event.

7.7.3 Duration of Response

Duration of response will be defined as the time from the date of first documented response, (that is subsequently confirmed (as defined in Section 7.7.2)) until date of documented progression or death in the absence of disease progression, the end of response should coincide with the date of progression or death from any cause used for the PFS endpoint. The time of the initial response will be defined as the latest of the dates contributing towards the first visit response of PR or CR.

If a subject does not progress following a response, then their duration of response will use the PFS censoring time.

7.7.3.1 Disease control rate

Disease control rate is defined as the proportion of patients with a best overall response of CR, PR or SD.

7.7.4 Change in tumour size

Tumour size is defined as the sum of the lengths of the longest diameters of the RECIST 1.1 target lesions. Percentage change in tumour size will be determined for patients with measurable disease at baseline and is derived at each visit by the percentage change in the sum of the diameters of TLs compared to baseline.

For further details see Appendix F of this Clinical Study Protocol.

7.7.5 Overall Survival

Overall survival will be assessed based on the date of first dose and survival status at the time of analysis.

Overall survival is defined as the interval between the date of first dose and the date of patient death due to any cause. Patients who have not died at the time of the statistical analysis will be censored at the time they were last known to be alive.

7.7.6 Tumour Response by independent central review

For the independent central review, the same RECIST 1.1 definitions will be applied, and programmatic details will be detailed in the Independent Review Charter.

7.8 Description of analysis sets

The analysis of data will be based on different subsets according to the purpose of the analysis. Throughout the safety results sections, erroneously treated patients (eg, those assigned to receive dose A who actually received dose B, those who failed to meet the selection criteria) will be accounted for in the actual dose group received.

Analysis sets are presented in Table 7

Table 7Analysis sets

Analysis Set	Definition
Safety	All patients who received at least 1 dose of AZD9291.
Pharmacokinetics	Dosed patients who have at least 1 measurable plasma concentration collected post-dose.
Evaluable for response	Dosed patients with a baseline RECIST assessment.
Exploratory biomarkers	All patients that participate in the exploratory biomarker research

Analysis Set	Definition
Paired biopsy	Dosed patients with a pre-study tumour biopsy and one tumour biopsy on study treatment

7.9 Methods of statistical analysis

The statistical analyses will be performed by or other designated third party providers, under the direction of the

With the exception of some safety and PK summaries that may be combined, data from the dose escalation and the dose expansion cohorts will be presented separately. Data from the extension cohort will always be presented separately. Summaries from the extension cohort will be presented as a cohort and by previous treatment cohort (TKI only or TKI plus additional treatments).

The intent of all efficacy analyses from the expansion phase is that it be focussed on the population whose tumour T790M mutation status is identified via central testing. Patients central test results must match the cohort expansion group to which they were assigned (i.e. T790M+ in the 1st expansion). However, concordance between local and central testing of T790M status will be reviewed, and if deemed appropriate summaries incorporating local testing status may be produced. All summaries will present data by dose group.

Demographic data

Characteristics of the patients, including medical history and disease characteristics at baseline will be listed for each patient and summarised by dose group.

Reasons for discontinuation of investigational product will be listed including the study day of treatment discontinuation and will be summarised by dose group.

Exposure

Exposure to investigational product ie, total amount of study drug received will be listed for all patients.

Total exposure and total time on study (date of last dose minus date of first dose) will be summarised by the following: mean, standard deviation, minimum, maximum, median and number of observations. In addition, the number and percentage of patients with at least one dose interruption/dose delay and at least one dose reduction will be presented separately for the initial period defined as 21 days of multiple dosing (cycle 1) and for any time following this initial period of the study.

Safety

Safety data will not be formally analysed. All patients who receive at least one dose of AZD9291 will be included in the assessment of the safety profile (safety analysis set). At the end of the study, appropriate summaries of all safety data will be produced, as defined below.

Data from all cycles of initial treatment will be combined in the presentation of safety data. AEs will be listed individually by patient and dose group. For patients who have a dose modification, all AEs (due to drug or otherwise) will be assigned to the initial dose group. The number of patients experiencing each AE will be summarised by the Medical Dictionary for Regulatory Activities (MedDRA) system organ class, MedDRA preferred term and CTCAE grade. The number and percentage of patients with adverse events in different categories (eg, causally related, CTCAE grade \geq 3 etc) will be summarised by dose group, and events in each category will be further summarised by MedDRA system organ class and preferred term, by dose group. SAEs will be summarised separately if a sufficient number occur.

Any AE occurring before the first dose of investigational product (ie, before study Day 1) will be included in the data listings but will not be included in the summary tables of adverse events.

Any AE occurring within the defined 28 day follow-up period after discontinuation of investigational product will be included in the AE summaries. Any adverse events in this period that occur after a patient has received further therapy for cancer (following discontinuation of investigational product) will be flagged in the data listings. AEs occurring after the 28 day follow-up period after discontinuation of investigational product will be listed separately, but not included in the summaries.

Haematology, clinical chemistry, vital signs, ECG data, ophthalmic examination data, demographic data and concomitant medications will be listed individually by patient and suitably summarised. For all laboratory variables, which are included in the current version of CTCAE, the CTCAE grade will be calculated. Summary statistics of mean, median, standard deviation, minimum, maximum and number of observations will be used.

Details of any deaths will be listed for all patients.

Any qualitative assessments will be summarised for all patients using the number of patients with results of negative, trace or positive.

Graphical presentations of safety data will be presented as is deemed appropriate. This may include, but is not restricted to, presentation of parameters against time, concentration or shift plots. Appropriate scatter plots will also be considered to investigate trends in parameters compared to baseline.

Pharmacokinetics

Plasma concentrations of AZD9291, AZ5104 and AZ7550 will be summarised by nominal sample time. Plasma concentrations and derived PK parameters will be summarised by dose level. Parameters following single and multiple dosing will be summarised separately. Plasma concentrations at each time point will be summarised according to dose by the following summary statistics:

- The geometric mean (gmean, calculated as $\exp [\mu]$, where μ is the mean of the data on a logarithmic scale)
- Coefficient of variation (CV, calculated as $100 \sqrt{[exp(s^2)-1]}$, where s is the standard deviation of the data on a log scale)
- Gmean \pm standard deviation (calculated as exp[$\mu \pm s$])
- Arithmetic mean calculated using untransformed data
- Standard Deviation calculated using untransformed data
- Minimum
- Maximum
- Number of observations

The following summary statistics will be presented for AUC, AUC₍₀₋₂₄₎, AUC_(0-t), AUC_{ss}, C_{max} , $C_{ss max}$ and $C_{ss min}$:

- Gmean, calculated as $exp[\mu]$, where μ is the mean of the data on a logarithmic scale)
- CV, calculated as $100 \sqrt{[\exp(s^2)-1]}$, where s is the standard deviation of the data on a log scale)
- Arithmetic mean calculated using untransformed data
- Standard deviation calculated using untransformed data
- Minimum
- Maximum
- Number of observations

The following summary statistics will be presented for CL/F, CL_{ss}/F, volume of distribution, $t_{1/2\lambda z}$, R_{AC} , time dependency:

Revised Clinical Study Protocol Drug Substance AZD9291 Study Code D5160C00001 Edition Number 3 Date

- Arithmetic mean
- Standard deviation
- Minimum
- Maximum
- Number of observation

The following summary statistics will be presented for t_{max} and t_{max ss}:

- Median
- Minimum
- Maximum
- Number of observations

The pharmacokinetic data for AZD9291, AZ5104 and AZ7550 after a single-dose and separately, at steady state will also be displayed graphically. Displays will include plasma concentration patient profiles (on the linear and log-scale) versus time and gmean concentration (+/-standard deviation) versus time, stratified by dose.

Scatter plots of PK parameters versus dose, or log-dose will also be considered following both single and multiple dose administration of AZD9291 to assess dose proportionality.

In a preliminary assessment of dose proportionality, log-transformed AUC and C_{max} parameter estimates will be examined using the Power Model:

parameter = $e^a (dose)^b$

ie, $\log(\text{parameter}) = a + (b * \log(\text{dose}))$

where a is the intercept, depending on patients, and b is the slope, measuring the extent of dose proportionality. Dose proportionality implies that $\beta=1$ and will be assessed by estimating β along with its confidence interval.

If there is evidence of departures from dose proportionality, log-transformed dose-normalised AUC and C_{max} , of AZD9291 will be analysed separately using a mixed effects model. Dose will be fitted as a fixed effect and patient as a random effect. Point estimates and associated 90% confidence intervals for the differences between each dose level and the reference dose (the lowest dose) will be constructed using the residual variance. The estimates will then be back-transformed to provide point estimates and corresponding 90% confidence intervals for the reference dose on the original scale. No adjustments for

Revised Clinical Study Protocol Drug Substance AZD9291 Study Code D5160C00001 Edition Number 3 Date

pre-planned multiple comparisons will be made. This analysis will only be performed provided there are sufficient data.

Pharmacodynamics

The pharmacodynamic effects of AZD9291 will be evaluated in tumour tissue from paired biopsies (A tumour biopsy pre-dose and a paired tumour biopsy post-dose). The biomarkers investigated may include, but are not limited to pEGFR, pERK, pAKT, pS6, pGSK3b, p4EBP1, cleaved caspase 3 and Ki67. The technological platform for the pharmacodynamic analysis will be immunohistochemistry, but may not be limited to this.

Exploratory biomarker research and pharmacogenetics

The number of patients that will agree to participate in the exploratory biomarker and genetic research is unknown. It is therefore not possible to establish whether sufficient data will be collected to allow a formal statistical evaluation or whether only descriptive statistics will be generated.

Patient Reports Outcomes

Analyses on the EORTC QLQ C-30 and QLQ-LC13 will be based on the instruments' scoring manual.

Tumour response

The analysis population for objective tumour response rate will be the "evaluable for response" population.

For the escalation cohorts, summaries of tumour response data will be by dose.

For the expansion cohorts, the summaries will be by dose and centrally confirmed T790M status (positive, negative, unknown). First line cohort(s) will be summarised separately to pre-treated cohorts. A sensitivity analysis may be performed using local T790M status for patients whose central T790M status is not available.

For the extension cohort, all summaries will be presented as a cohort and by previous treatment cohort (TKI only or TKI plus additional treatments).. For the primary objective all RECIST outcomes will be based on the independent central review, and ORR will be summarised for the patients who have measurable disease at baseline as defined by ICR.

Tumour response data will be listed and summarised by dose group, and if appropriate using the following response categories: Complete Response (CR), Partial Response (PR), Stable Disease (SD), Progressive Disease (PD) and Non-Evaluable (NE).

Objective tumour response rates will be presented together with 80% and 95% confidence intervals (calculated using the Clopper-Pearson interval), where appropriate.

Duration of response

For the expansion and extension cohorts duration of response in responding patients will be summarised and the number (%) of responding patients with a duration of response >3; >6; >9; >12 months will be presented. A Kaplan Meier plot and median duration of response with 95% CI (calculated from the Kaplan Meier plot) will be presented. DCR will be summarised with 95% confidence intervals.

Progression free survival and overall survival

The analysis population for progression free survival and overall survival will be the safety population.

PFS will be summarised for the expansion phase and the extension phase. OS will be summarised for the extension phase only.

PFS and OS will be displayed using Kaplan Meier plots. The number of events, median (calculated from the Kaplan Meier plot), and proportion of patients without an event at 6, 12 and 18 months will be summarised.

As appropriate, summaries of the number and percentage of patients who have died, are still in survival follow-up, are lost to follow-up and have withdrawn consent will be presented.

Sensitivity analysis:

The same methods of analysis will be applied to analyse ORR, DoR, DCR, tumour shrinkage and PFS based on the RECIST data assessed by the Investigator

Change in tumour size

The analysis population for change in tumour size will be the "evaluable for response" population who have measurable disease at baseline per RECIST 1.1 criteria

Summaries and waterfall plots (bar charts) indicating percentage change from baseline in the sum of the diameters of target lesions at week 6 may be produced, if appropriate, depending on how much data is obtained in patients with measurable disease at baseline. If there is only limited data then percentage change in tumour size will be listed only.

